2.2 INVESTIGATION OBJECTIVES

The primary objective of this investigation is to demonstrate the effectiveness of the SIFS in a lumbar interbody application. Effectiveness will be determined as a composite score that represents patient success. To be considered a patient success, each of the following criteria must be met at the 24-month study interval:

- Pain – Improvement in low back pain score evidenced by a 20 mm reduction on a 100 mm Visual Analog Scale (VAS) when compared to baseline (Note: a lower VAS pain score indicates less pain),
- Function – Improvement in low back function evidenced by a 15 point decrease of the Oswestry Disability Index (ODI) score compared to baseline. (Note: a higher ODI score indicates a greater disability with respect to low back function),
- Fusion – Bridging bone demonstrated on CT Scan
- Safety – Freedom from device-related Serious Adverse Events and secondary surgical interventions at the index level through the 24-month study interval.

In addition to the above stated primary objective, this investigation will yield data on the following outcomes, subject parameters and clinical utility:

- Variable scores over time (pain, function, fusion) as individual parameters
- Adverse Event rate(s) reported by relatedness and severity
- Neurological status over time
- Quantitative/qualitative radiographic data over time specific to the index level and contiguous levels (translation, angulation, disc height, and device position)
- Demographics
- Hospitalization Utility (duration of surgery, estimated blood loss and duration of hospitalization)
- Work status over time
- Pain medication use

Data collection is not limited to the above data points. Additional parameters will be reported on as appropriate. For a more detailed list of supplemental outcomes refer to Section 3.2 Scientific Soundness and Statistical Analysis.

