3.2.1 Primary Endpoint

The primary endpoint (success) is a composite endpoint of pain, function, fusion, and safety, defined as meeting each of the following criteria at the 24-month study interval:

- Pain – Improvement in low back pain score evidenced by a 20 mm reduction on a 100 mm Visual Analog Scale (VAS) when compared to baseline (Note: a lower VAS pain score indicates less pain),
- Function – Improvement in low back function evidenced by a 15 point decrease of the Oswestry Disability Index (ODI) score compared to baseline. (Note: a higher ODI score indicates a greater disability with respect to low back function),
- Fusion – Bridging bone demonstrated on CT Scan
- Safety – Freedom from investigational device-related Serious Adverse Events at the index level through the 24-month study interval.

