3.2.3 Statistical Methods

The statistical analysis of the data obtained from this study will be performed using SAS® version 9.1 or higher. All statistical tests will be performed at the 0.05 significance level, unless otherwise indicated.

Data collected in this study will be documented using summary tables and subject data listings. Continuous variables will be summarized using descriptive statistics, specifically the mean, median, standard deviation, minimum, and maximum, and a 95% confidence interval for the mean based

on the t-distribution. Categorical variables will be summarized using frequencies and percentages and 95% exact (Clopper-Pearson) confidence intervals for the true proportions.

All analyses of effectiveness and safety will be based upon the Treated Population defined to be all treated subjects.

3.2.4 *Determination of Sample Size*

The required sample size was calculated based on the following specifications:

1. Endpoint: success rate
2. One-sided exact binomial test for a binomial proportion
3. Alpha = 0.05
4. True percentage of successes = 68%
5. Performance Goal (null percentage of successes) = 55%
6. Power = 80%

The required sample size based upon these specifications is 87 subjects. The sample size was increased to 102 subjects to take into account an assumed 15% lost to follow-up rate.

3.2.5 *Sample Size Re-Estimation*

A sample size re-estimation will be performed based on 12-month interim data.

3.2.6 *Analysis of Primary Endpoint*

The primary endpoint for this investigation is a composite endpoint of pain, function, fusion, and safety that meets all of the following criteria at the 24-month study interval:

- Pain – Improvement in low back pain score evidenced by a 20 mm reduction on a 100 mm Visual Analog Scale (VAS) when compared to baseline (Note: a lower VAS pain score indicates less pain),
- Function – Improvement in low back function evidenced by a 15 point decrease of the Oswestry Disability Index (ODI) score compared to baseline. (Note: a higher ODI score indicates greater disability with respect to low back function),
- Fusion – Bridging bone demonstrated on CT Scan
- Safety – Freedom from investigational device-related Serious Adverse Events at the index level through the 24-month study interval.

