This endpoint will be summarized using the count and percentage, together with a 95% exact (Clopper-Pearson) confidence interval for the true proportion of successes. The null and alternative hypotheses for this endpoint are as follows:

$$H_0: p \leq 0.55$$

versus

$$H_1: p > 0.55$$

where p denotes the true proportion of subjects achieving success for this endpoint. The null hypothesis will be tested using a 1-sided exact binomial test for a binomial proportion conducted at the 0.05 level of significance.

Missing values for the primary endpoint at Month 24 will be imputed using the last-observation-carried-forward (LOCF) method and multiple imputation methods. For subjects who are missing at most one component of the primary endpoint at Month 24 and who have a value for the given component at Month 12, the LOCF method will be used to impute a value for that component at Month 24, so that the value of the primary endpoint at Month 24 can then be determined. Once the LOCF procedure has been performed, multiple imputation methods will be used to impute values for the remaining subjects with missing values for the primary endpoint at Month 24. The imputation procedure will be based on primary endpoint data at all previous post-baseline time points.

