On-Site Monitoring – An in-person evaluation of the clinical investigation site that is conducted by sponsor personnel or representatives.

Other Related AE – An adverse event that occurs and is determined to have a relatedness that is not device, hardware general surgery or unknown relatedness.

Procedure Related AE – An adverse event that occurs as a result of the surgical procedure. A procedure related AE may occur as a result of one or more of the following and shall be specified as such for analysis and reporting purposes:

- *Procedure – Device*: Occurs due to the implantation procedure for the investigational device (SIFS mesh)
- *Procedure – Hardware*: Occurs due to the implantation procedure for the supplemental fixation
- *Procedure – General Surgery*: Occurs as a result of the general surgical procedure

Removal – A surgical procedure in which all of the original system (intervertebral device plus supplemental fixation) confirmation is removed, with or without replacement.

Re-Operation – Any surgical procedure at the treated level that does not include removal, modification, or addition of any implanted components.

Revision: Device – A surgical procedure that adjusts or in any way modifies or removes part of the original intervertebral implant configuration, with or without replacement of a component. A revision may also include adjusting the position of the original configuration.

Revision: Hardware – A surgical procedure that adjusts or in any way modifies or removes part of the original supplemental fixation implant configuration, with or without replacement of a component. A revision may also include adjusting the position of the original configuration.

Risk-Based Monitoring – A dynamic assessment procedure that systematically approaches clinical trial monitoring of the individual and global investigation sites, evaluating for data integrity, observable trending and compliance risks that may be associated with the clinical investigation during the trial lifecycle.

Serious Adverse Event (SAE) – An adverse event that requires hospitalization, prolongs or extends the hospitalization, is life-threatening, results in a congenital anomaly/birth defect, or results in death. The device-relatedness or procedure-relatedness of such an event will be adjudicated by the DMC.

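### The primary objective counts index-level secondary surgery as failure, but the endpoint that is tested does not

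*Combined protocol and SAP*

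**What the plan says.** Section 2.2 (Investigation Objectives) lists four criteria, all of which must be met at 24 months for a subject to be a success. The safety criterion is "Freedom from device-related Serious Adverse Events and secondary surgical interventions at the index level through the 24-month study interval".

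Sections 3.2.1 (Primary Endpoint) and 3.2.6 (Analysis of Primary Endpoint) repeat the pain, function and fusion criteria. Their safety criterion is "Freedom from investigational device-related Serious Adverse Events at the index level through the 24-month study interval". Secondary surgery appears in neither.

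Section 3.2.6 then sets up the only hypothesis test in the plan, H0: p ≤ 0.55 against H1: p > 0.55, "where p denotes the true proportion of subjects achieving success for this endpoint". The additional outcomes in 3.2.2 and 3.2.7 are descriptive, and secondary surgery is not among them.

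Section 3.2.4 sizes the study with a performance goal of 55% and "True percentage of successes = 68"%, without saying which safety definition these refer to. Section 3.2.5 adds: "A sample size re-estimation will be performed based on 12-month interim data".

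Section 11.0 defines an SAE as "An adverse event that requires hospitalization, prolongs or extends the hospitalization, is life-threatening, results in a congenital anomaly/birth defect, or results in death". It defines a hardware revision as "A surgical procedure that adjusts or in any way modifies or removes part of the original supplemental fixation implant configuration" (with or without replacement, and including repositioning) and a re-operation as "Any surgical procedure at the treated level that does not include removal, modification, or addition of any implanted components". It also defines removal and device revision. No available section groups these under the term secondary surgical intervention.

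**The concern.** In a single-arm performance-goal study, the definition of success is the claim. Here the objective and the test use different definitions, so rejecting H0 under 3.2.6 would not by itself show that the objective in 2.2 was met.

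The definitions also decide how many subjects count as failures. If the choice between them is left until data are in hand, it becomes a post-hoc choice of primary endpoint. The planned re-estimation on 12-month data makes the timing matter.

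A second ambiguity lies inside the criterion that is kept. If two sections define device related differently, the same SAE can pass or fail the safety component even when 3.2.6 is followed to the letter.

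**Working it through.** **1. Does another section close the gap?**

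- *SAE definition (8.2 and 11.0).* The criteria are hospitalization, prolonged hospitalization, threat to life, congenital anomaly and death. Surgery is not itself a criterion.
- *Relatedness (8.1).* Hardware-related events form a separate class from device-related events, and 3.2.6 counts only the latter. Surgery for a fixation problem, or surgery adjudicated as general-surgery, other or unknown related, does not fail 3.2.6 even if it leads to hospitalization.
- *Narrow reading of 2.2.* If device-related is taken to qualify the surgeries as well as the SAEs, the gap shrinks to device-related index-level surgery that meets no SAE criterion. It does not vanish.

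The discordant subjects are those who had index-level surgery, had no device-related SAE, and still met the pain, function and fusion criteria. This group is smaller than everyone who had secondary surgery.

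**2. Is device related consistently defined?**

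| Place | Harm from implanting the mesh |
|---|---|
| 8.1, relatedness list | Not in device related (presence or performance of the mesh only); classed as Procedure – Device |
| 11.0, Device Related | Included in device related |
| 11.0, Procedure Related AE | Classed as Procedure – Device |

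**3. The plan's own sample size.** Inputs from 3.2.4: p0 = 0.55, p1 = 0.68, one-sided alpha 0.05, exact binomial test. The pass mark r is the smallest count with P(X ≥ r | n, 0.55) ≤ 0.05.

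- n = 87: r = 56, size 0.0487, power P(X ≥ 56 | 87, 0.68) = 0.801. The stated 87 subjects and 80% power reproduce.
- n = 102: r = 65, size 0.0464, power 0.849 if all 102 are observed.

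**4. How many reclassified subjects change the verdict?** Start from the planned rate: 0.68 × 87 = 59.16, about 59; 0.68 × 102 = 69.36, about 69. Then move subjects from success to failure and compute P(X ≥ k | n, 0.55).

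| Moved | n = 87: successes, p | n = 102: successes, p |
|---|---|---|
| 0 | 59, 0.0101 | 69, 0.0063 |
| 1 | 58, 0.0179 | 68, 0.0110 |
| 2 | 57, 0.0302 | 67, 0.0184 |
| 3 | 56, 0.0487 | 66, 0.0298 |
| 4 | 55, 0.0752 (fails) | 65, 0.0464 |
| 5 | – | 64, 0.0697 (fails) |

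The verdict flips at 4/87 = 4.6 points or 5/102 = 4.9 points. At the pass mark itself, one subject flips it.

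**5. Power if 68% was set for the 3.2.6 definition and the wider one is adopted.** Let q be the assumed share of discordant subjects. Power is P(X ≥ r | n, 0.68 − q).

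| q | n = 87 | n = 102 |
|---|---|---|
| 0 | 80.1% | 84.9% |
| 1 point | 74.0% | 79.2% |
| 2 points | 67.1% | 72.5% |
| 3 points | 59.7% | 64.9% |
| 5 points | 44.3% | 48.4% |

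**6. False-positive risk if 55% was set for the 2.2 definition.** If the true success rate under 2.2 is exactly 55%, the rate under 3.2.6 is 55% + q. At n = 87 the 3.2.6 test then rejects with probability 4.9%, 7.1%, 10.0%, 13.6% or 23.6% for q = 0, 1, 2, 3 or 5 points.

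Every q is an assumption, and all figures treat outcomes as fully observed, whereas 3.2.6 plans last-observation-carried-forward and multiple imputation.

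**The case against.** The strongest reply is that the test is not ambiguous about secondary surgery. Sections 3.2.1 and 3.2.6 agree word for word, and the hypotheses are tied to that wording. If 55% and 68% were set for it, the test keeps its size and power, and the defect is one clause in the objectives. That is right as far as it goes, but 3.2.4 does not say which definition the figures belong to. Nor does any section say that 3.2 overrides 2.2. If it does, 2.2 promises something the test does not show.

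Three other points have force. Device-related in 2.2 may govern both nouns, and a device-related surgery that requires hospitalization already fails 3.2.6; the gap is then small. Discordant subjects must also meet the pain, function and fusion criteria, so the shares above must not be read as secondary-surgery rates, and 3 of 87 or 4 of 102 such subjects leave the verdict at the planned rate unchanged. And Section 8.1 presents its relatedness definitions as the ones to be applied, with the Procedure Related entry in 11.0 in agreement, so the Device Related entry in 11.0 is the outlier. These limit the likely effect. They do not remove either contradiction.

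The Data Monitoring Committee charter and the case report forms are not in the available text and might define secondary surgical intervention. They could not make 2.2 and 3.2.6 say the same thing.

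**Conclusion.** The concern holds and should be corrected before any endpoint analysis. The contradiction between 2.2 and 3.2.1/3.2.6 is textual and certain, and so is the conflict over device related. Together they leave open who counts as a success under the stated objective and who fails the safety component of the study's only confirmatory test.

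The numerical effect is unknown, because no secondary-surgery rate is given. At the planned success rate a few discordant subjects would not matter; near the pass mark a single one would. Whether the mismatch costs power, raises the false-positive risk against the 2.2 definition, or affects only the wording of the claim depends on which definition 55% and 68% were set for.

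**What to change.** Before the 12-month re-estimation and any endpoint analysis:

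1. Reconcile 2.2, 3.2.1 and 3.2.6 to a single safety component. If secondary surgical intervention stays, define it through the Section 11.0 categories (removal, device revision, hardware revision, re-operation) and state whether device-relatedness is required. If it goes, reword 2.2 to match.
2. Reconcile device related between 8.1 and the two entries in 11.0, so that an SAE from mesh implantation has one classification.
3. State which definition the 55% goal and the 68% assumption refer to, and restate power if the reconciled definition differs.
4. Preferably, report the composite under the other definition as a sensitivity analysis, together with the index-level secondary-surgery rate. This is useful but not needed to cure the inconsistency.

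The cost is a wording amendment to three sections and the definitions. Section 8.0 already has treatment required recorded for each adverse event; whether a form field must change cannot be judged without the case report forms. Adopting the wider definition can only leave the success rate unchanged or lower it, with the loss of power illustrated above unless 68% already allowed for it. Keeping the narrower one means that 2.2 can no longer count freedom from secondary surgery as part of patient success.

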2.3 STUDY DURATION

This study will conclude when the final study subject has achieved their 24-month study evaluation. While the primary endpoints for this trial are defined at 24 months post-operative, this investigation will include annual subject self-assessment follow-ups at 36 months and 48 months post-operative while study enrollment is ongoing. This means that subjects enrolled into this investigation are expected to achieve a final (physical) study examination that includes imaging and neurological testing approximately 24-months after their index procedure. Following the 24-month physical evaluation and testing that supports primary endpoint analysis, subjects are expected to complete a self-assessed Patient Survey Form and a Long-Term Follow-Up Questionnaire at the 36-month and 48-month timepoint as appropriate until the final study subject has completed study participation at the 24-month timepoint. Therefore, while a subject's active participation (physical examination/testing) may conclude at 24-months post-op, their study participation may extend to include longer-term remote follow-up to a maximum of 48-months post-operative resultant of the potential for the self-administered survey/questionnaire completion.

It is anticipated that the enrollment phase of this investigation shall be complete within approximately eighteen (18) to twenty-four (24) months (1.5 to 2 years) of initiation and that the overall study shall conclude in approximately 42-months (3.5 years) to 48-months (4 years) based on the following estimations:

- Although the study is approved to be conducted at a maximum of 15 investigative sites, ideally, the study shall be conducted at approximately 10 of the 15 investigative sites.
- It is anticipated that a full patient complement (enrollment) will consist of no more than 102 subjects.
- Each investigative site is expected to enroll approximately 10 subjects (.85 subjects per month/10 subjects per year yielding an anticipated total enrollment duration of 12 months per site. It is recognized that should enrollment be protracted, it may potentially require up to 18 months (1.5 years) to enroll the complete cohort.
- Allowing for staged site activation (2 - 3 sites per month x 10 sites), it is anticipated the cumulative duration of enrollment would be approximately 18 months to 24 months.
- Accounting for the 24-month follow-up, it is anticipated the total study duration will be between 42-months (3.5 years) and 48-months (4 years) from initiation to closure.

3.0 INVESTIGATION DESIGN

3.1 OVERVIEW AND GENERAL DESIGN

This is a FDA regulated, prospective, non-randomized, single treatment arm, multicenter, IRB approved performance goal investigation designed to evaluate the safety and effectiveness of the SIFS mesh device when implanted in the intervertebral body disc space with bone graft during an instrumented lumbar fusion procedure. Enrolled subjects will be evaluated for device safety and effectiveness outcomes that support primary endpoint analysis through the 24-month time point. As previously noted in the protocol, study subjects will be expected to complete a self-administered survey annually through a maximum of 48 months post-operative as necessary until the last study subject has concluded study participation. Data from this investigation will be used to support a regulatory submission (e.g., *De novo* petition).

This non-randomized investigation will examine the primary endpoint and numerous additional outcomes. A Data Monitoring Committee will be established for this trial and shall oversee trial conduct to ensure the safety and protection of study participant rights and welfare. An independent core lab will be utilized to perform fusion assessments and radiologic measurements.

3.2 SCIENTIFIC SOUNDNESS AND STATISTICAL ANALYSIS

The safety and effectiveness of the SIFS will be evaluated utilizing standard statistical practices and principles.

3.2.1 Primary Endpoint

The primary endpoint (success) is a composite endpoint of pain, function, fusion, and safety, defined as meeting each of the following criteria at the 24-month study interval:

- Pain – Improvement in low back pain score evidenced by a 20 mm reduction on a 100 mm Visual Analog Scale (VAS) when compared to baseline (Note: a lower VAS pain score indicates less pain),
- Function – Improvement in low back function evidenced by a 15 point decrease of the Oswestry Disability Index (ODI) score compared to baseline. (Note: a higher ODI score indicates a greater disability with respect to low back function),
- Fusion – Bridging bone demonstrated on CT Scan
- Safety – Freedom from investigational device-related Serious Adverse Events at the index level through the 24-month study interval.

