3.2.2 Additional Outcomes

Beyond supporting the primary endpoint of this investigation, Spineology is evaluating additional outcome data. The investigation design allows for the assessment of objective and subjective findings. Descriptive data will be provided to characterize these additional effectiveness and safety measures:

- Mean low back VAS pain score over time through the 24-month interval
- Mean lower extremity (right and left leg) VAS scores over time through the 24-month interval
- Mean ODI score over time through the 24-month interval
- Fusion at the 12-month and the 24-month interval
- Occurrence of device-related Serious Adverse Events through the 24-month interval
- Occurrence of study-related Adverse Events through the 24-month interval
- Neurological status assessment (strength, sensation, and reflexes) over time through the 24-month interval (reporting categorized as improved, maintained, or reduced with new or increased neurological deficit being further categorized as transient (< 3 months/90 days) or longer term \geq 3 months/90 days);
- Radiographic data observed over time specific to the index level (translation, angulation, disc height, and device position)
- Subject satisfaction with procedure/outcome
- Work status over time
- Pain medication use over time
- Operative time
- Estimated blood loss
- Duration of hospitalization
- Graft site pain (as applicable)
- Adjacent segment status at 24-months post-operative assessed by quantitative and qualitative radiographic data (translation, angulation, and disc height)

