7.2 RISKS

7.2.1 SIFS Mesh Risks

The potential risks associated with the study device include but are not limited to:

- Mesh disruption (tear)
- Device migration
- Allergic reaction to PET

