8.1 Adjudication Procedure

Each AE will be reviewed individually by a DMC/CEC. The DMC Charter is provided as **Appendix V**. Each event is initially classified as an adverse event or a non-event. A non-event is an event that does not require treatment. An event captured and determined to be a non-event will be reported as an observation. Following this determination, an adverse event is assessed for relatedness to the trial and may be classified as a study-related adverse event or a not-study-related adverse event. A not-study-related adverse event is an adverse event determined to not have a causal relationship with either the device or the procedure. All study-related adverse events are further adjudicated for severity and relatedness to the procedure/device as defined below.

Event severity refers to the degree of seriousness of the AE. The categories of event severity are: Serious Adverse Event (SAE) and a rating of mild, moderate or severe. Event relatedness refers to the association to the investigational device, fixation hardware or the surgical procedure. Event relatedness is categorized by the following associations: device related, hardware related, procedure related, other related, or unknown (undeterminable) relatedness.

For clarification, the following “relatedness” definitions will be applied in this investigation:

- **Device Related:** An adverse event that results from the presence or performance of the SIFS mesh device.
- **Hardware Related:** An adverse event that results from the presence or performance of any of the supplemental fixation device components.
- **Procedure Related:** A procedure related adverse event shall be evaluated and adjudicated in accordance with the below sub-classifications. A procedure related AE may occur as a result of one or more of the following and shall be specified as such for analysis and reporting purposes:
 - *Procedure – Device:* Occurs due to the implantation procedure for the investigational mesh device
 - *Procedure – Hardware:* Occurs due to the implantation procedure for the supplemental fixation
 - *Procedure – General Surgery:* Occurs as a result of the general surgical procedure and is not related to any of the above defined definitions or any of the below definitions.
- **Other Related:** An adverse event that occurs and is determined to have a relatedness that is not device, hardware, procedure, general surgery, or unknown relatedness.

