9.4 DATA MONITORING COMMITTEE (DMC)

An independent Data Monitoring Committee will be established for this investigation and will function as an advisory group to provide independent oversight of the investigation and to ensure patient safety. The DMC shall be comprised of no less than three (3) physician consultants of appropriate training, expertise and experience in the spinal discipline and a biostatistician. A DMC Chairperson shall be designated to preside over DMC meetings. The DMC may function in the role of a Data Safety Monitoring Board (DSMB) and as a Clinical Events Committee (CEC). The complete DMC Charter is provided as **Appendix V**.

DMC DSMB primary responsibility is to ensure subject safety. Additional DMC DSMB responsibilities may include, but are not limited to, review of interim analyses of outcomes, safety data summaries and study performance information. In addition, the DMC DSMB may provide recommendations relative to the study design, stopping rules for trial conduct, and determinations for continuance, modification, or termination of investigation conduct. DMC DSMB meetings will be conducted no less than annually.

DMC CEC responsibilities include review and adjudication of all adverse events reported for this investigation. The DMC CEC shall adjudicate events for seriousness, relatedness and severity. The DMC CEC shall review all events for potential UADE occurrence. DMC CEC meetings shall be conducted on a quarterly basis throughout the duration of this investigation.

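### The primary safety component counts device-related SAEs only at the index level, so on a plain reading a serious mesh reaction elsewhere in the body would not fail it

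*Combined protocol and SAP*

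**What the plan says.** The safety component is worded identically where the primary endpoint is defined (3.2.1) and where it is analysed (3.2.6): "Freedom from investigational device-related Serious Adverse Events at the index level through the 24-month study interval".

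Section 2.2 words the same component differently: "Freedom from device-related Serious Adverse Events and secondary surgical interventions at the index level through the 24-month study interval". There the index-level phrase comes directly after the surgical interventions.

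Three other parts of the protocol bear on the point:

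- **Cause.** Section 8.1 defines a device-related event as "An adverse event that results from the presence or performance of the SIFS mesh device". Section 11.0 adds the implantation procedure but also goes by cause. Neither definition mentions location, and nor does the SAE definition in 8.2.
- **Descriptive outcome.** Section 3.2.2 lists "Occurrence of device-related Serious Adverse Events through the 24-month interval" with no limit on level. Section 3.2.7 reports it by subject with an exact confidence interval.
- **Known risks.** Section 7.2.1 names three mesh risks, one of which is "Allergic reaction to PET".

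On adjudication, 9.4 states: "The DMC CEC shall adjudicate events for seriousness, relatedness and severity". The relatedness categories in 8.1 do not include spinal level.

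**The concern.** Once the committee has judged an SAE to be caused by the mesh, where in the body it appears does not make it less of a device harm. With the index-level limit attached to the SAE criterion, a subject admitted to hospital with a systemic reaction to the mesh material could appear in the device-related SAE table and still be counted as meeting the safety component of the composite. If that subject also met the pain, function and fusion criteria, the result would be a success in the trial's only hypothesis test.

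Any such misclassification runs in one direction. The limit can remove failures from the composite but cannot add them. It also brings in a classification, index level or not, for which the protocol body gives no rule and names no decision-maker.

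**Working it through.** **Step 1. What the phrase can attach to.** In 2.2 the criterion names two things, device-related SAEs and secondary surgical interventions, and the phrase follows the second. An anatomical limit is natural for an intervention. In 3.2.1 and 3.2.6 the interventions are absent and the phrase remains, so the SAEs are the only thing left for it to qualify.

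**Step 2. A test case.** Take a systemic reaction to PET that requires hospitalization.

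| Question | Section | Answer |
|---|---|---|
| Serious? | 8.2 | Yes, by hospitalization |
| Device related? | 8.1, 11.0 | Yes, by cause |
| In the descriptive device-related SAE outcome? | 3.2.2, 3.2.7 | Yes |
| Fails the primary safety component? | 3.2.1, 3.2.6 | Not on the plain wording, because it is not at the index level |

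**Step 3. Reproduce the plan's sample size.** The inputs, from 3.2.4, are a "One-sided exact binomial test for a binomial proportion", alpha 0.05, null 0.55, alternative 0.68 and power 80%. For each n, take the smallest r with P(X ≥ r | 0.55) ≤ 0.05, then compute power at 0.68. The first n to reach 80% is 87, with r = 56, exact alpha 0.0487 and power 0.801. This agrees with the plan. Dividing by 0.85 gives 87/0.85 = 102.35, against the stated 102. No figure in the plan is in dispute.

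**Step 4. Size per subject.** The primary analysis uses all treated subjects, with imputation, so the denominator is close to 102. Each affected subject who otherwise succeeds adds 1/102 = 0.98 percentage points.

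**Step 5. Sensitivity.** The documents give no rate for these events. Assume that a share q of otherwise successful subjects has one, with q from 0.5% to 5%. Two quantities follow at n = 87, r = 56:

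- If the rate counting all device-related SAEs is exactly 0.55, the rate as worded is 0.55/(1 − q). The chance of passing is then P(X ≥ 56 | 87, 0.55/(1 − q)).
- If 0.68 is the rate as worded, counting all device-related SAEs makes it 0.68(1 − q). Power is then P(X ≥ 56 | 87, 0.68(1 − q)).

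| q | Chance of passing when the all-location rate is 0.55 | Power if all device-related SAEs count |
|---|---|---|
| 0 | 0.0487 | 0.8010 |
| 0.5% | 0.0541 | 0.7812 |
| 1% | 0.0601 | 0.7605 |
| 2% | 0.0738 | 0.7162 |
| 3% | 0.0901 | 0.6686 |
| 5% | 0.1322 | 0.5667 |

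For scale, 0.68 × 102 = 69.4 successes are expected. So q = 1% means about 0.7 affected subjects (69.4 × 0.01) and q = 5% about 3.5 (69.4 × 0.05). The lower rows of the table would need several such events in one trial.

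**The case against.** The strongest reply is that the phrase was never meant as a limit. Only one level is treated and the mesh is implanted only there, so the words may simply say where the device sits. They may also be left over from the 2.2 sentence once the interventions were dropped. Either is possible and no text rules it out. But no text states it either, and the unrestricted wording in 3.2.2 makes it harder to treat the phrase as empty. This reply lowers confidence that a restriction was intended. It does not remove the need to settle the wording.

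A second reply is that nothing is hidden. All events are captured and adjudicated, and 3.2.7 reports device-related SAEs wherever they occur. That is right, so the problem is confined to classification within the composite. Known PET sensitivity is also a contraindication (1.5), and an affected subject must still meet the other three criteria to be an overall success.

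Four stronger readings are tempting and are not supported:

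- *The primary endpoint contradicts 3.2.2.* It does not. A descriptive outcome may be broader than a primary component. The inconsistency in wording is between 2.2 and 3.2.1/3.2.6.
- *The independent committee does not decide level.* The charter is Appendix V and is not reproduced in the text available. Only the silence of the protocol body can be shown.
- *One such subject could reverse the conclusion.* At n = 102 the p-value is 0.0464 for 65 successes and 0.0697 for 64. At n = 87 it is 0.0487 for 56 and 0.0752 for 55. But misclassifying any one subject at the boundary of an exact test does the same, so this says nothing particular about the present wording.
- *Harm from a displaced mesh would escape the component.* This is arguable. Section 6.0 defines expulsion as movement out of the disc space, so the failure starts at the treated segment and could be classed there. The systemic reaction is the clearer example.

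**Conclusion.** The point holds as a defect of definition. On the plain wording of 3.2.1 and 3.2.6, an SAE adjudicated as caused by the mesh but located away from the treated segment does not fail the primary safety component, although relatedness is defined by cause alone. Section 2.2 differs, and the protocol body does not say who assigns level.

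The size is probably small: about 1 percentage point of the success rate for each affected subject who meets all the other criteria, always in the device's favour. At an assumed q of 0.5% to 2%, the chance of passing when the all-location rate is exactly 55% rises from 4.9% to between 5.4% and 7.4% at n = 87. Those rates are assumptions, and the larger values in the table should not be used to argue for greater severity. The conclusion rests on the restrictive reading of the phrase, which is the plain one but not the only one.

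**What to change.** Delete the index-level phrase from the device-related SAE criterion in 3.2.1 and 3.2.6, so that any SAE adjudicated as device-related through 24 months fails the safety component. In the same edit, reconcile 2.2 so that the phrase qualifies only the secondary surgical interventions. Device-related SAEs then need no assignment to a level, which also removes the question of who would make it.

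The cost is four words in each of two sections and a rewording of one sentence in 2.2, with no new data collection. The observed success rate may be slightly lower. If the phrase was meant only to say where the device is implanted, deleting it loses nothing. The change should be made before 24-month outcomes are known.
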